9. EFFICACY ANALYSES

9.1. Overview of Planned Efficacy Analyses

Following review of the data, additional analyses may be conducted to further support the evaluation and interpretation of the data. Details of data displays being presented in Section [11.10](#): List of Data Displays.

9.1.1. Endpoints / Variables

The following endpoints will be analysed:

- Change from Baseline in Weighted Mean AUC (0-120) C-Peptide & Glucose from MMTT
- Change from Baseline in Weighted Mean AUC [(60-140)] C-Peptide & Glucose from Hyperglycemic Clamp Test
- Change from Baseline in Insulin Sensitivity Index from Hyperglycemic Clamp Test
- Change from Baseline in Mean Daily Insulin Use
- Change from Baseline in %HbA1c
- Change from Baseline in Body Weight
- Hypoglycemic and hyperglycemic events over Months 1-24.
- Number (percent) of participants meeting responder status on C-peptide from MMTT
- Number (percent) of participants achieving partial remission status
- Number (percent) of participants achieving HbA1c Responder Status

For detailed derivations of the efficacy endpoints please see Section [11.5.4](#).

9.1.2. Summary Measure

For continuous measures the treatment comparison will be the difference between treatment means at each visit. If log transformation is required the treatment comparison will be the ratio of treatment means at each visit.

For responder endpoints the treatment comparison will be the difference in % of responders in each treatment group.

9.1.3. Population of Interest

The efficacy analyses will be based on the Intent-To-Treat (Treated) population, unless otherwise specified.

9.1.4. Strategy for Intercurrent (Post-Randomization) Events

No imputation of missing data will be performed.

9.1.5. Statistical Analyses / Methods

Details of the planned displays are provided in Section [11.10](#): List of Data Displays and will be based on GSK data standards and statistical principles.

Unless otherwise specified, endpoints / variables defined in Section [9.1.1](#) will be summarised using descriptive statistics, graphically presented (where appropriate) and listed.

Responder endpoints will be summarised only.

9.1.5.1. Statistical Methodology Specification - MMRM

Endpoints

 • Change from Baseline in Weighted Mean AUC (0-120) C-Peptide & Glucose from MMTT • Change from Baseline in Weighted Mean AUC [(60-140)] C-Peptide & Glucose from Hyperglycemic Clamp Test • Change from Baseline in Insulin Sensitivity Index from Hyperglycemic Clamp Test • Change from Baseline in Mean Daily Insulin Use • Change from Baseline in %HbA1c • Change from Baseline in Body Weight
Model Specification

 • Endpoints will be statistically analysed using a mixed model repeated measures (MMRM) model. 
Terms fitted in the MMRM model will include:
 
 • Fixed Categorical: Treatment, Visit, Treatment * Visit Interaction • Fixed Continuous Covariates: Baseline # • Repeated: Visit 
Other covariates may be added using the following procedure:
 
For each covariate the MMRM model for the MMTT C-peptide analysis using the ITT population will be expanded and fitted two times:
 
 1. Only the covariate will be added as an additional fixed factor 2. Both the covariate and the interaction of the covariate with treatment will be added as fixed factors 
If the covariate is significant at a 10% alpha level using Type III p-values in the first model, then the covariate may be added to all MMRM models of efficacy endpoints or specific analyses may be repeated with the covariate added. When the interaction between the covariate and treatment is significant at a 10% alpha level in the second model, then both the covariate and the interaction of the covariate with treatment may be added.
 
The following covariates will be considered: BMI, Weight, Number of positive Auto Antibodies (categorical, 1 or > 1; see Section 11.5.3 for derivation).
 
The p-values for the tests described above will be presented in the statistical listing for the MMTT C-peptide analysis.

Model Checking Assumptions

 • Model assumptions will be applied, but appropriate adjustments may be applied based on the data. • The Kenward and Roger method for approximating the denominator degrees of freedom and correcting for bias in the estimated variance-covariance of the fixed effects will be used.

- An unstructured covariance structure for the R matrix will be used by specifying 'type=UN' on the REPEATED line.
 - In the event that this model fails to converge, alternative correlation structures may be considered such as Spatial Power Model, CSH or CS. The correlation structure chosen should make sense and not just chosen because model converges (e.g. AR(1) would not be appropriate as the visit structure is not even).
 - Akaike's Information Criteria (AIC) will be used to assist with the selection of covariance structure.
- Distributional assumptions underlying the model used for analysis will be examined by obtaining a normal probability plot of the residuals and a plot of the residuals versus the fitted values (i.e. checking the normality assumption and constant variance assumption of the model respectively) to gain confidence that the model assumptions are reasonable.
- If there are any departures from the distributional assumptions, alternative models will be explored using appropriate transformed data.
- All model checking will be presented in a statistical listing along with the raw SAS output from the analyses.

Presentation of Results

- Adjusted means (Value and Change from Baseline) and corresponding standard error of means (SEs) and 95% confidence intervals will be presented for each treatment by time, together with estimated treatment differences and the corresponding 95% confidence intervals.
- Plots of LS means \pm SE from the model will be generated for each treatment by time. Additionally, plots of differences and 95% confidence intervals for the comparison of interest will be generated.

Sensitivity and Supportive Analyses

- A supportive analysis using the 'Fully Treated' population will be performed for the following endpoints:
 - Change from Baseline in Weighted Mean AUC (0-120) C-Peptide & Glucose from MMTT
 - Change from Baseline in Weighted Mean AUC (60-140) C-Peptide & Glucose from Hyperglycemic Clamp Test

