In contrast, in two Phase III trials (DEFEND 1&2, respectively), where a substantially reduced dosage regimen of otelexizumab was investigated (total dose of 3.1 mg vs. 48-64 mg in the BDR proof-of-concept study), no effect on C-peptide or any key secondary or exploratory endpoints were observed. Likewise, in the Phase III trial Protégé, lower doses of teplizumab relative to the proof-of-concept study (0.1, 0.2, 0.4, 0.8, 10 X 1.6 mg per day, 17.5 mg cumulative dose compared to 34.9 mg in the Herold study) failed to demonstrate a statistically significant treatment effect on a range of metabolic endpoints. However, although some trends were observed with respect to C-peptide and insulin requirements, the duration of apparent efficacy was reduced (6 months vs. 12 months). Thus, the relationship between dose, duration of treatment, and magnitude and duration of efficacy has not been fully elucidated with any anti-CD3 antibody. However, the current weight of clinical evidence suggests that a high and sustained degree of blockade of CD3 is required during the dosing period to achieve a clinically relevant and durable response in halting the disease progression of NOT1DM patients.

In addition to dose, several post-hoc analyses (BDR, Herold and Protégé studies [Sherry, 2011; Herold, 2005]) have suggested that time to treat following disease diagnosis and age of the patient are key determinants of treatment response, with teplizumab preserving C-peptide secretion only in T1DM patients treated within 6 weeks from the diagnosis [Sherry, 2011; Herold, 2005].

Therefore, the efficacy measured on the degree of β -cell preservation efficacy seems to be strictly dose and time from diagnosis dependent, with the younger population (<27 years old) being more responsive (BDR and Protégé studies).

It is anticipated that the therapeutic window for anti-CD3 therapy is fairly narrow with the immediate risk of tolerability related to increased severity of cytokine release syndrome (CRS) at higher doses and the longer-term risk related to EBV reactivation. Therefore, the aims of this study are to explore the safety, tolerability, pharmacokinetics, pharmacodynamics, efficacy and immunological profile of escalating repeat doses of intravenously administered oteelixizumab in NOT1DM patients. The data obtained from this study will inform the design of subsequent efficacy studies.

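### SAP 9.1.5.1 lets 10% tests on MMTT C-peptide pick optional covariates and interactions, so the reported MMRM is not fixed and the C-peptide intervals fall somewhat below nominal coverage

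*SAP*

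**What the plan says.** SAP 9.1.5.1 defines the base model under "Terms fitted in the MMRM model will include": treatment, visit, their interaction, and baseline, with visit as the repeated factor. It then adds a selection step. "For each covariate the MMRM model for the MMTT C-peptide analysis using the ITT population will be expanded and fitted two times": once with the covariate alone, once with the covariate and its interaction with treatment. The candidates are limited: "The following covariates will be considered: BMI, Weight, Number of positive Auto Antibodies (categorical, 1 or > 1".

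The consequence of passing is permissive. For a main effect, the trigger is "If the covariate is significant at a 10% alpha level using Type III p-values in the first model", and the consequence is "then the covariate may be added to all MMRM models of efficacy endpoints or specific analyses may be repeated with the covariate added". For an interaction, the trigger is "When the interaction between the covariate and treatment is significant at a 10% alpha level in the second model", after which both terms may be added.

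The SAP does not say:
- which of the two permitted actions will be taken;
- what happens if several candidates pass (BMI is calculated from weight, SAP 11.5.2);
- whether the base-model result remains the main one;
- at what covariate value a treatment difference is read once an interaction is in the model.

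The list of displays (SAP 11.10.7) has one MMRM table per endpoint and population, none labelled by covariate set. The selection p-values will be listed (SAP 9.1.5.1 and Listing 54). The tables give 95% intervals and p-values against placebo (SAP 9.1.5.1 and shell EFF_T2), with no multiplicity adjustment (SAP 5.3).

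**The concern.** Two separate problems follow.

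First, interval validity. When the C-peptide data choose the terms and the same data then supply the estimates, the standard errors take no account of the choice. A covariate kept because it happened to reduce residual variance gives an interval that is too narrow. An interaction kept by chance moves the estimated treatment difference.

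Second, discretion. Protocol 5.4 makes site, CRO and sponsor staff unblinded (while restricting the randomisation code itself to the pharmacist), and Protocol 9.3.1.1 has the study team reviewing unblinded efficacy data as the trial proceeds. An optional model choice is made by people who can see where it leads. Protocol 1.1 intends these data to inform the design of later efficacy studies, so the C-peptide estimates by dose matter even though C-peptide is a secondary endpoint.

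**Working it through.** The plan states no power, coverage or error rate for the efficacy MMRM, so there is no figure to reproduce. The check is how the stated rule behaves.

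**Inputs from the documents.** Three candidates and six tests at 0.10 (SAP 9.1.5.1). Allocation 8:2 per cohort (Protocol 3.1), placebo pooled (SAP 5.1), three doses reported. Pooled placebo is 3 × 2 = 6, giving arms of 6/8/8/8 if cohort 3 filled.

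**Assumptions not in the documents.** Cohort 3 size 8 (also 5); BMI–weight correlation 0.8 (also 0.5); 70% of patients with more than one antibody (also 85%); true covariate effects of 0, 0.3 or 0.5 residual SD; no treatment effect.

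**How often something is selected.** If the tests were independent and no covariate mattered:
- three main effects: 1 − 0.9³ = 0.271;
- all six tests: 1 − 0.9⁶ = 0.469.

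The tests overlap, so the simulated rates are lower: 23% to 25% for any main effect, 18% to 24% for any interaction, and 40% to 42% for at least one of the six.

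**Simulation.** A single-visit ANCOVA stands in for the MMRM, with 6,000 trials per scenario. Baseline is always in the model. Main effects are tested by a 1-df F-test and interactions by a 3-df F-test, both at 0.10. All passing terms enter together. 95% t-intervals against placebo are read at the mean covariate value. Ranges run across six scenarios.

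| MMTT C-peptide model reported | Coverage of nominal 95% interval |
|---|---|
| Base model | 94.5% to 95.4% |
| Main effects added by rule | 93.7% to 94.3% |
| Main effects and interactions added by rule | 92.7% to 93.5% |
| Trials in which an interaction was selected | 88% to 90% |
| Most favourable permitted model | 89.0% to 92.4% |

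Monte Carlo error is roughly 0.3 to 0.5 points. It is larger in the fourth row, which rests on about a fifth of trials: at most about √(0.89 × 0.11 / 1,300) = 0.9 points. In the last row, the four scenarios with no true covariate effect give 91.9% to 92.4%; 89.0% occurs with true effects of 0.5 SD. When a noise main effect is selected, the interval is about 5% narrower than the base-model interval (width ratio 0.950 to 0.956).

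**Other endpoints.** Selecting on C-peptide and analysing a different outcome gives coverage of 95.1%, 94.9% and 94.2% at residual correlations of 0, 0.3 and 0.6 with C-peptide.

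**Price of fixing the model.** If the covariates do nothing, pre-specifying all three keeps coverage at 94.8% to 95.0%, but intervals widen by 7% to 8% (for example 2.408 / 2.243 = 1.07). If they are prognostic, base-model intervals are wider than those under main-effect selection: 2.436 / 2.297 = 1.06 at 0.3 SD and 2.757 / 2.378 = 1.16 at 0.5 SD. Part of that gap arises because the selected-model intervals are too short.

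**Estimability of the antibody interaction.** The chance that some arm has nobody in one antibody category is 1 − ∏(1 − pⁿ − (1 − p)ⁿ) over n = 6, 8, 8, 8. For p (the share with more than one antibody) of 0.6, 0.7, 0.8 and 0.9 this is 10%, 26%, 58% and 91%.

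**The case against.** The case for leaving the text alone is reasonable. Base terms, candidates, outcome, population and threshold are all named in advance, and the selection p-values are disclosed. One of the two permitted actions, rerunning specific analyses, is already a sensitivity analysis in all but name. C-peptide is secondary, no formal hypotheses are tested (SAP 2.4), and multiplicity is openly uncontrolled. With five visits and assumed between-visit correlations of 0.5 to 0.85, a no-effect trial shows at least one of three dose comparisons below 5% at a given visit about 12% of the time, and at some visit 26% to 39% of the time. A two-point coverage loss is small beside that. The simulation is also a simplification resting on assumed inputs.

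Most of this stands as a limit on severity. It does not remove the point: the stated approach is estimation and inference, interval coverage is what selection damages, and disclosing p-values does not say which model will be in the table.

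A reader might infer four stronger things that the documents do not support.
- *All MMRM intervals are too narrow.* Only MMTT C-peptide is both selected on and estimated; the other endpoints inherit terms chosen on a different outcome.
- *The model is reopened by unblinding.* SAP 4.1 mentions an unblinding step, but under Protocol 5.4 staff are unblinded throughout. The model is also only partly open.
- *Adding Weight distorts the Body Weight analysis.* If baseline weight is meant, the term duplicates one already present and leaves the treatment estimates unchanged.
- *Age has to be added.* Protocol 1.1 does say that "time to treat following disease diagnosis and age of the patient are key determinants of treatment response", but as a suggestion from post-hoc analyses. Inclusion criteria 1 and 2 already restrict age to 16–27 years and treatment to within 32 days of diagnosis. A main-effect term would also not address a modifier of response. Requiring age would be a preference.

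**Conclusion.** The concern holds, limited to two statements. The SAP does not fix which MMRM its tables will show. For MMTT C-peptide, the selection rule gives intervals below nominal coverage: about 93% under mechanical use, 88% to 90% when an interaction is selected, and 89% to 92% if discretion is used to report the most favourable permitted model. Interactions and the optional wording cause more of the loss than main effects do. The figures depend on the single-visit ANCOVA simplification, arms of 6/8/8/8 and the assumed covariate distributions; varying these moved results only within the ranges shown. An interaction does not make the treatment difference meaningless, since at the mean covariate value a linear interaction model still estimates the sample-average difference. That value has to be stated, however. This is a cheap improvement; it does not undermine the trial.

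**What to change.** In SAP 9.1.5.1, state that:
- the base model (treatment, visit, treatment-by-visit, baseline) is the main analysis for every MMRM endpoint and is always the model in the main tables and figures;
- models with BMI, Weight or antibody count, with or without treatment interactions, are reported only as labelled sensitivity analyses, giving the covariate value at which treatment differences are evaluated;
- Weight is left out of the Body Weight model as redundant with baseline.

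The selection p-values can still be listed. No age term is needed.

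The cost is a few lines of SAP text and some precision in the main model if a candidate is truly prognostic: slight for weak effects, more noticeable for strong ones, as the width ratios above show. The sensitivity models would still display that gain.

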9.2. Overview of Planned Pharmacodynamic Analyses

9.2.1. Endpoints / Variables

The following endpoints will be analysed:

- Relative change from baseline (%) in CD4+ and CD8+ cells, free CD3 and bound oteelixumab on CD4+ and CD8+ cells on Days 1 through 14.

9.2.2. Summary Measure

The target engagement variables (see Section [11.5.5](#) for a detailed listing and derivations) will be summarized. The treatment comparison will be the difference between treatment means at each visit.

9.2.3. Population of Interest

The pharmacodynamic analyses will be based on the Fully Treated Population unless otherwise specified. Listings will be created using the Safety Population.

9.2.4. Strategy for Intercurrent (Post-Randomization) Events

No imputation of missing data will be performed.

9.2.5. Statistical Analyses / Methods

Analysis will be restricted to summary statistics. Details of the planned displays are provided in Section [11.10](#) List of Data Displays and will be based on GSK data standards and statistical principles.

9.3. Pharmacokinetic / Pharmacodynamic Analyses

No PK/PD Analyses are considered to be in the scope of this RAP.

9.4. Overview of Planned Exploratory Analyses

9.4.1. Endpoints / Variables

The following endpoints will be analysed as available:

- Frequency and phenotype of lymphocyte subsets by flow cytometry
- Frequency and phenotype of lymphocyte subsets by flow cytometry by C-peptide Responder Status
- Frequency and phenotype of HLA-A2-restricted T1D- and EBV-specific CD8+ T cells by multimer analysis
- Quantification of serum cytokines and soluble cytokine receptors
- Percentage Productive clonality by TCR deep sequencing

Due to data quality the remaining biomarker data will be listed only:

Details of data displays being presented in Section [11.10](#).

Further details of the endpoints to be considered is presented in Section [11.8](#).

9.4.2. Summary Measure

For continuous measures the treatment comparison will be the difference between treatment means at each visit. If log transformation is required the treatment comparison will be the ratio of treatment means at each visit.

9.4.3. Population of Interest

Figures will be based on the Fully Treated Population. For the other outputs the ITT Population will be used, with the exception of the multimer analysis, which will be performed using the Multimer Analyses Population.

9.4.4. Strategy for Intercurrent (Post-Randomization) Events

No imputation of missing data will be performed.

9.4.5. Statistical Analyses / Methods

Analysis will be restricted to summary statistics. Details of the planned displays are provided in Section [11.10](#): List of Data Displays and will be based on GSK data standards and statistical principles.

11. APPENDICES

11.1. Appendix 1: Schedule of Activities**11.1.1. Protocol Defined Time & Events****11.1.2. Screening**

Medication history
Full physical examination (including height and weight)
Drug/alcohol history
Chest X-ray (to rule out TB)
Serology (EBV, HIV, Hep C, Hep B, Syphilis)
12-lead ECG in triplicate
Vital signs (including temperature, blood pressure and pulse rate (in triplicate) and respiration rate
Urine Pregnancy test (female only)
Haematology (must include total lymphocyte count)
Clinical Chemistry
T1DM Auto antibody (Anti-GAD, anti-IA2, antibody to islet cell antigen (ICA), anti-Zn T8)
EBV Viral Load (PCR)
AE assessment

The following must be performed at least 7 days prior to dosing
Mixed Meal Stimulated C-peptide (MMTT)

11.1.3. Dosing and Follow-Up

	Day											Month								36 month (if applicable) and/or final follow up		
	-2	-1	1	2	3	4	5	6	14	21	Week 4	Week 6	2	3	6	9	12	18	24			
Patient admitted to unit ¹	X																					
In Patient		X	X	X	X	X ²	X ²	X ²														
Prophylaxis then IV Dosing of study treatment			X	X	X	X	X	X														
Patient Discharged ²								X														
Out Patient#						X	X	X	X	X		X	X	X	X	X	X	X	X			
Telephone call or out-patient visit to collect AEs, hypoglycemic and hyperglycemic events and concomitant medication use											X											X
Brief Physical Examination		X	X ³	X ³	X ³	X ³	X ³	X ³	X	X		X	X	X	X	X	X	X	X			
12 lead ECG ^{4,6}		X	X	X	X	X	X	X	X								X		X			
Vital Signs ^{5,6}		X	X	X	X	X	X	X	X	X		X	X	X	X	X	X	X	X			
Serum Pregnancy Test		X										X	X	X	X	X	X	X	X			
Alcohol & drugs of abuse test		X																				
Haematology ⁷		X		X	X	X	X	X	X	X		X	X	X	X	X	X	X	X			
Clinical Chemistry ⁷		X	X	X	X	X	X ⁸	X				X		X	X	X	X	X	X			
HSV-1 & HSV-2 IgG & IgM ⁹		X																				
EBV Viral Load (PCR) ⁷		X						X		X		X	X	X	X ¹⁰							X
EBV Serology - IgG and IgM ⁷		X						X		X		X	X	X	X		X		X			
CMV Serology - IgG and IgM ⁷		X						X				X	X	X	X		X		X			

	Day										Month								36 month (if applicable) and/or final follow up	
	-2	-1	1	2	3	4	5	6	14	21	Week 4	Week 6	2	3	6	9	12	18		24
PK Blood Sample ⁶			X	X	X	X	X	X	X ¹¹											
CD3 Saturation, free CD3 bound otelixizumab /CD4+/CD8+ Blood Sample ⁶			X	X	X	X	X	X	X ¹¹											
Record insulin usage for 7 days before visit / call		X							X	X	X	X	X	X	X	X	X	X	X	X
AE Assessment			←-----→																	
Concomitant Medication Review			←-----→																	
Hypoglycaemic / Hyperglycaemic Events			←-----→																	
Anti-GAD, anti-IA2, antibody to islet-cell antigen (ICA), anti-ZnT8 & Insulin-antibodies (IAA)		X																		
Anti-otelixizumab antibodies Blood Sample		X											X	X						
Mixed Meal Stimulated C-peptide (MMTT) ¹²													X	X ¹⁴		X	X	X ¹⁴		
Beta Cell Function by Hyperglycaemic Clamp ¹³		X												X ¹⁴				X ¹⁴		
HbA1c		X												X		X		X		X ¹⁵
Bodyweight		X										X	X	X	X	X	X	X	X	
Various Blood samples for Exploratory Biomarkers		X						X ¹⁶				X		X	X		X		X ¹⁷	
Saliva sample for Pharmacogenetics (PGx) ¹⁸			←-----→																	

#Patients will record insulin usage for 7 days prior to out-patient visits (up to Month 24) and before telephone call/visit in Month 36 (if applicable) or final follow up.

Significant AEs including hypoglycaemic (≤3.9 mmol/L; ≤70 mg dL) and hyperglycaemic (>13.9 mmol/L; >250 mg/dL) events will be recorded in a diary whenever they occur, to include start and stop dates.

1. Patient admitted evening of Day -2
2. Discharged on Day 6 if health considered satisfactory by the investigator. Dosing Day 4-6 may be performed on out-patient basis

3. Physical exam performed to monitor for changes in clinical status
4. ECG pre-dose (in triplicate), at the end of the infusion and 6 hours post start infusion (if infusion < 6 hours)
5. Vital signs include temperature, blood pressure and pulse rate (in triplicate), and respiration rate
6. See Section 6.2.3 of the CSP for timings
7. Pre-dose on dosing days
8. If LFTs have shown an upward trend continue to monitor daily after day 6
9. HSV-1 & HSV-2 IgG & IgM will be measured at Day -1 and during the study if clinically indicated
10. If still positive at 6 months EBV viral load will be monitored every 3 months until month 24
11. One sample during visit
12. Blood samples for C-peptide and glucose levels collected at -10, 0, 15, 30, 60, 90 and 120 minutes
13. Plasma C-peptide and glucose levels will be measured during the hyperglycaemic clamp procedure at the following time points: L150, L165 and L180 minutes [during the euglycaemic (L)ow phase], H0, H60, H90, H120 and H140 minutes [during the hyperglycaemic (H)igh phase]
14. Mixed Meal and Glucose Clamp must be separated by at least 4 days
15. Patients will be asked to report verbally their HbA1c at Month 36 (if applicable) and/or final follow-up; followed eventually (if available) by a printed result via regular mail (or scan electronically).
16. Limited biomarkers on Day 6 pre-dose
17. Blood samples for exploratory biomarkers will only be analysed at Month 24 if indicated based on Month 12 results
18. One PGx (DNA) saliva sample taken between Day 1 and 6

11.1.4. Detail for Vitals, ECG and PK & PD Monitoring over the Infusion Period (Cohorts 1-4)

Day	Cohort	Assessment	Pre Dose	0 H	30 M	1 H	2 H	3 H	4 H	5 H	6 H	7 H	8 H	9 H	10 H	11 H	12 H	13 H	14 H	15 H	16 H			
1	C1	Dosing																						
		Vitals ^{1,2}	X	X		X	X	X	X	X	X	X	X	X	X	X	X	X	X				X	
		ECG	X									X			X									
		PK/CD3 Saturation	X		X	X	X		X		X		X	X									X	
	C2-C4	Dosing																						
		Vitals ^{1,2}	X	X		X	X	X	X	X	X	X	X	X	X	X	X	X	X	X	X	X	X	
		ECG	X									X						X						
		PK/CD3 Saturation	X		X	X		X		X		X					X					X		
2	C1-C4	Dosing																						
		Vitals ^{1,2}	X	X		X	X	X	X	X	X	X	X	X	X	X		X					X	
		ECG	X									X												
		PK/CD3 Saturation	X																					
3	C1-C4	Dosing																						
		Vitals ^{1,2}	X	X		X	X	X	X	X	X	X	X	X				X					X	
		ECG	X					X				X												
		PK/CD3 Saturation	X																					

Day	Cohort	Assessment	Pre Dose	0 H	30 M	1 H	2 H	3 H	4 H	5 H	6 H	7 H	8 H	9 H	10 H	11 H	12 H	13 H	14 H	15 H	16 H	
4	C1-C4	Dosing																				
		Vitals ^{1,2}	X	X		X	X	X ³														
		ECG	X			X		X ³														
		PK/CD3 Saturation	X																			
5	C1-C4	Dosing																				
		Vitals ^{1,2}	X	X		X	X	X ³														
		ECG	X			X		X ³														
		PK/CD3 Saturation	X																			
6	C1-C4	Dosing																				
		Vitals ^{1,2}	X	X		X	X	X ³														
		ECG	X			X		X ³														
		PK/CD3 Saturation	X			X																

1. Blood pressure to be taken in triplicate at Pre-dose
2. Vitals to be repeated at 30 min intervals should there be any safety concern
3. If patients are dosed on an out-patient basis on Day 4, 5 and 6, vital signs and ECGs will stop after the 3 hour post dose time point (if the Investigator is satisfied with the clinical status of the patient), if there are any concerns then vital signs and ECGs may be continued as judged necessary by the investigator until the investigator is satisfied

Day	Cohort	Assessment	Preferably within first hour of visit, time to be recorded in eCRF
14	C1-C4	PK/CD3 Saturation	X

